### **Outcome Measures**

#### **Primary Outcome**

The primary outcome was the incidence of major intra-abdominal complications within two months following surgery. Major complications were predefined as:

- Adhesive small bowel obstruction requiring intervention
- Enterocutaneous fistula
- Reoperation for intra-abdominal complication
- Grade  $\geq 3$  wound complications based on the Clavien–Dindo classification

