#### **Secondary Outcomes**

Secondary outcomes included:

- Individual complication rates, including intraperitoneal adhesions, bowel obstruction, surgical site infection, incisional hernia, and fistula formation

- Time to bowel function recovery, defined as the time to first flatus and tolerance of oral diet
- Length of intensive care unit (ICU) stay and total hospital stay
- Device-related adverse events, including infection, inflammatory reaction, or mesh-related complications
- Radiologic assessment of adhesions or obstruction using magnetic resonance imaging (MRI) at baseline, one month, and two months
- Quality of life assessment using the European Organisation for Research and Treatment of Cancer Quality of Life Questionnaire Core 30 (EORTC QLQ-C30), a validated cancer-specific instrument [20]

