### Statistical Analysis Plan

Statistical analyses were performed using SPSS version 29.0 (IBM Corp., Armonk, NY, USA). Continuous variables were assessed for normality using the Shapiro–Wilk test and are presented as mean  $\pm$  standard deviation for normally distributed data or median with interquartile range for non-normally distributed data. Between-group comparisons were conducted using the independent t-test or Mann–Whitney U test for continuous variables and the chi-square test or Fisher’s exact test for categorical variables, as appropriate. Effect estimates for the primary and key secondary binary outcomes were expressed as relative risks with 95% confidence intervals. Time-to-event outcomes, including time to bowel function recovery, were analyzed using Kaplan–Meier survival curves with log-rank testing. Multivariable logistic regression analysis was performed to adjust for potential confounders, including age, primary tumor type, peritoneal cancer index score, and use of hyperthermic intraperitoneal chemotherapy. All statistical tests were two-sided, and a p-value  $< 0.05$  was considered statistically significant. Analyses were conducted on an intention-to-treat basis.

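### The p < 0.05 rule covers every outcome, so roughly 11 to 14 secondary comparisons can be called significant with no control of the overall error

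*Combined protocol and SAP*

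**What the plan says.** The Primary Outcome section names one endpoint: "The primary outcome was the incidence of major intra-abdominal complications within two months following surgery".

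The Secondary Outcomes section lists six groups. The first is "Individual complication rates, including intraperitoneal adhesions, bowel obstruction, surgical site infection, incisional hernia, and fistula formation", which is worded as an open list. The others are time to bowel function recovery ("defined as the time to first flatus and tolerance of oral diet"), two lengths of stay (intensive care and total hospital), device-related adverse events, MRI at baseline and at one and two months, and the EORTC QLQ-C30, with no scale or time point chosen.

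The Statistical Analysis Plan then applies a single decision rule: "All statistical tests were two-sided, and a p-value" below 0.05 counts as statistically significant. Relative risks with 95% confidence intervals are promised for the "primary and key secondary binary outcomes", but no section says which secondaries are key. There is no test order, no adjustment, no condition that the primary succeed first, and no statement that secondaries are supportive or exploratory.

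**The concern.** Read literally, the rule gives a p-value of 0.04 on hospital stay or on one MRI visit the same standing as a p-value of 0.04 on the primary outcome. With this many comparisons, at least one chance finding is likely even if the mesh does nothing. Because the key secondaries are not named, they could be chosen after the results are known.

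This matters more here than in a well-powered trial. If the primary outcome misses 0.05, which is quite possible with 30 patients per arm, attention moves to the secondaries. The plan's own rule would then call any of them below 0.05 significant.

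**Working it through.** **The plan's own figures.** The plan states no familywise error rate, so there is none to reproduce. Its only computed design figure is 26 per group (Sample Size Calculation). With p1 = 0.40, p2 = 0.20, two-sided 0.05 and 80% power, its formula gives (1.960 + 0.842)² × (0.24 + 0.16) / 0.20² = 78.5, so 79 per group. That is a separate problem. It enters here only through the power in step 5.

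**1. Number of comparisons.** Device-related events are left out, because the control arm receives no biomaterial and there is nothing to compare. The logistic regression is also left out, because the plan does not say which outcome it applies to. One QLQ-C30 score is assumed.

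| Counting choice | Complications | Bowel recovery | Stay | MRI | QLQ-C30 | Total |
|---|---|---|---|---|---|---|
| Bowel recovery as one endpoint, MRI once per visit | 5 | 1 | 2 | 2 | 1 | 11 |
| Flatus and diet separate, MRI once per visit | 5 | 2 | 2 | 2 | 1 | 12 |
| Bowel recovery as one endpoint, MRI adhesions and obstruction separate at each visit | 5 | 1 | 2 | 4 | 1 | 13 |
| Flatus and diet separate, MRI adhesions and obstruction separate at each visit | 5 | 2 | 2 | 4 | 1 | 14 |

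**2. Familywise error with k independent tests, all nulls true, each of exact size 0.05:** 1 − 0.95^k.

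- k = 11: 43.1%
- k = 12: 46.0%
- k = 13: 48.7%
- k = 14: 51.2%

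**3. Effect of correlation.** Equally correlated normal test statistics were simulated (400,000 draws, two-sided 0.05). The correlations are assumptions; the documents give none.

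| Common correlation | 12 tests | 13 tests |
|---|---|---|
| 0.3 | 40% | 42% |
| 0.5 | 32% | 33% |
| 0.7 | 23% | 24% |

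**4. Effect of Fisher's exact test.** At 30 per arm its actual size, by enumeration, is 0.15% at a common event rate of 5%, 0.9% at 10%, 2.2% at 20% and 2.6% at 30 to 40%. Take 12 independent tests, of which seven are binary (five complications and two MRI readings, assumed present or absent) and five have size 5%:

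- all binary rates 5%: 1 − (1 − 0.00147)^7 × 0.95^5 = 23%
- all binary rates 20%: 1 − (1 − 0.0222)^7 × 0.95^5 = 34%
- all binary rates 30%: 1 − (1 − 0.0261)^7 × 0.95^5 = 36%

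The event rates are assumptions. These figures use Fisher's test throughout. The chi-square test, which the plan also allows, has size close to 5% at rates of 10% and above, and would bring the result nearer to step 2.

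**5. Power of the primary test at n = 30 per arm** (pooled normal approximation): Φ{[(p1 − p2)√n − 1.96√(2p̄(1 − p̄))] / √[p1(1 − p1) + p2(1 − p2)]}, where p̄ is the mean of p1 and p2.

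- 0.40 versus 0.20: (1.095 − 1.270) / 0.632 = −0.276, so 39%
- 0.45 versus 0.15, the most favourable pair in the stated ranges: (1.643 − 1.270) / 0.612 = 0.609, so 73%

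**The case against.** The strongest reply is that a small trial with one primary outcome commonly leaves its secondaries unadjusted. The primary objective is tied to a single prespecified endpoint, and the plan already promises confidence intervals for some secondaries. It is true that formal adjustment is not obligatory. But the usual practice relies on secondaries being understood as supportive. This plan does not say so, and its significance rule says the opposite.

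The second reply is that the independent-test figures are too high. This stands in part. Adhesions and obstruction appear both clinically and on MRI, MRI is repeated, and intensive care stay is part of hospital stay, so positive correlation is likely. Sparse binary outcomes tested with Fisher's exact test rarely reach 5% size. Steps 3 and 4 show the reduction, and neither brings the rate near 5%.

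The third reply is that the count is a matter of interpretation, which also stands. If MRI were a single comparison and bowel recovery one endpoint, there would be 10 tests and 40.1% under independence. Several QLQ-C30 scales would push the count above 14. A reader might add device-related events to the 12-test count, reach 13, and treat 13 as a minimum and the resulting 49% as a maximum. The documents support neither. That item has no control-arm counterpart, and the bound for 13 tests under arbitrary dependence is 13 × 0.05 = 65%.

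**Conclusion.** The point holds as a gap in the decision rule for secondary outcomes. About 11 to 14 comparisons at 0.05 carry a 43 to 51% chance of at least one false significant result, assuming independence, all nulls true and exact 5% size. Under the assumed correlations of 0.3 to 0.7 the figure for 13 tests is about 42 to 24%. Conservative exact tests also lower it. Under every assumption examined it remains several times 5%.

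Two stronger inferences are not supported. A reader might infer that the primary result is inflated. It is not: there is one primary outcome, and testing secondaries does not change its type I error. A reader might also infer that the primary will fail and the trial will rest its claim on a secondary. The 39% power applies at 0.40 versus 0.20, whereas 0.45 versus 0.15 gives about 73%, and the documents do not say how a missed primary would be reported. What they do is leave that route open.

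**What to change.** In the Statistical Analysis Plan, replace the general significance sentence with wording such as: *Statistical significance at the two-sided 0.05 level is claimed for the primary outcome only. All secondary outcomes are supportive; they are reported as effect estimates with 95% confidence intervals, without adjustment for multiplicity, and are not described as statistically significant.* Either name the key secondary outcomes or drop the term.

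The plan specifies an effect estimate only for binary outcomes. An estimate with its interval should therefore also be named for bowel recovery, lengths of stay and quality of life.

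This changes wording and reporting only, and needs no new data or patients. The cost is that fewer secondary results can be claimed as significant. The change remains usable if data have already been seen, because it involves no choice among endpoints. Holm testing of a few named key secondaries after a significant primary is an optional extra, and only if they are named before the data are seen.

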**Data Management and Ethical Considerations**

All data were prospectively collected using standardized case report forms and anonymized prior to analysis. Data integrity was ensured through regular monitoring and cross-verification. The study included a predefined plan for de-identified individual participant data (IPD) sharing upon reasonable request following publication.

